/08		(1/3 meter) as outlined in the ATS Procedures Manual.
709	3.	8.1 Masked Examiner
710	The M	asked Examiner must be certified to test VA and stereoacuity. Because the Masked
711	Exami	ner must be masked to the subject's treatment group, he/she must be someone other than the
712	manag	ing clinician (in many cases the managing clinician will be the investigator but this is not
713	require	ed).
714	3.9	16-Week visit
715	This v	isit is only for children randomized to continued spectacle treatment who opt to receive
716	binocu	lar treatment at the 8-week visit. At the 16-week visit, children will have the same testing as

described in *section 3.8*; however, testing does not need to be completed by a masked examiner.

718 Following this visit, the study will end for these children.

719 **3.10** Non-Study Visits and Treatment

- 720 Investigators may schedule additional visits at their own discretion. Subjects will continue to
- follow the study-specified follow-up schedule regardless of any non-study visits. No data will be
- 722 collected at non-study visits for the purpose of the study.
- 723

Investigators must not start any additional treatment (other than that outlined in *section 3.1*) prior tothe 8-week outcome visit.

727 CHAPTER 4: MISCELLANEOUS CONSIDERATIONS IN FOLLOW-UP

728 4.1 Contacts by the Jaeb Center for Health Research and Sites

729 The Jaeb Center serves as the PEDIG Coordinating Center. The Jaeb Center will be provided with

the parent's contact information. The Jaeb Center may contact the parents of the subjects.

- Permission for such contacts will be included in the Informed Consent Form. The principal purpose
- of the contacts will be to develop and maintain rapport with the subject and/or family and to help
- coordinate scheduling of the outcome examinations.
- 734

735 The site investigator or coordinator will contact the parents of each subject after the first week of

- the study to encourage compliance with treatment (spectacle or binocular) and to confirm that there
- are no technical problems playing the binocular game for those assigned to binocular treatment.

738 4.2 Subject Withdrawals

739 Parents may withdraw their child from the study at any time. This is expected to be a very

- 740 infrequent occurrence in view of the study design's similarity to routine clinical practice and short
- duration. If the parents indicate that they want to withdraw their child from the study, the
- investigator personally should attempt to speak with them to determine the reason. If their interest
- is in transferring the child's care to another eye care provider, every effort should be made to
- comply with this and at the same time try to keep the child in the study under the new provider's
- 745 care.

746 4.3 Management of Refractive Error

747 Because of the short duration of the study and the requirement to have a cycloplegic refraction

- 748 within 7 months prior to enrollment, no cycloplegic refraction is mandated during the study.
- 749 Nevertheless, whenever the investigator suspects that refractive error may not be corrected
- according to study guidelines, a cycloplegic refraction should be performed. Change in spectacle
- correction is at investigator discretion, but must be prescribed according to the guidelines described
- in *section 2.2.1*. and spectacles will be paid for by the study.
- 753
- 754 Contact lenses are not allowed during the study.

755 4.4 Management of Strabismus

Because of the short duration of the study and the age group being studied, strabismus surgery is not
allowed prior to the end of the study. If surgery is performed, the date and type of surgery will be
recorded in the comment section of the Follow-up Examination Form.

759 **4.5 Risks**

760 **4.5.1 Development of Manifest Ocular Deviation or Diplopia**

- 761 Diplopia is expected to be rare based on our experience during the previous ATS18 study
- 762 comparing binocular treatment with patching. ²⁵
- 763
- 764 Data on frequency of diplopia will be collected from the child and parent(s) at each study visit.
- 765766 If treatment precipitates the development of a manifest ocular deviation (e.g., esotropia) and/or
- 767 diplopia, the parent will be advised to have the subject see the investigator as soon as possible. If a
- new manifest deviation is confirmed on examination, the decision as to whether to continue or
- 769 discontinue therapy will be left to the investigator's and parent's decision. If the investigator
- determines that binocular diplopia is present, continuation of treatment is also at the discretion of
- the investigator and parent(s). If amblyopia treatment is to be discontinued during the study, a

- 772 Protocol Chair should be called to discuss the case. Subjects discontinuing treatment during the
- 773 study will continue to be seen for the remaining regularly scheduled study visits.

774 4.5.2 Risks of Examination Procedures

- 775 The procedures in this study are part of daily eye care practice in the United States and pose no 776 known risks. As part of a routine usual-care exam, the subject may receive cycloplegic/dilating eye
- 777 drops.

778 4.5.3 Delay in Use of Traditional Amblyopia Treatment

- 779 The subjects in the either treatment group will not be able to perform any patching, atropine,
- 780 Bangerter filter, or additional vision therapy treatment during the study.

781 4.6 **Reporting of Adverse Events**

782 No surgical procedures are part of the protocol. There are no expected long-term adverse events 783 associated with playing the computer game on the iPad. Investigators will abide by local IRB 784 reporting requirements.

785 4.6.1 Risk Assessment

786 It is the investigators' opinion that the protocol's level of risk falls under DHHS 46.404 which is 787 research not involving greater than minimal risk.

788 4.7 **Discontinuation of Study**

789 The study may be discontinued by the Steering Committee (with approval of the Data and Safety 790 Monitoring Committee) prior to the preplanned completion of enrollment and follow-up for all 791 subjects.

792 4.8 **Travel Reimbursement**

- 793 Parents of each subject will be compensated \$40 per visit (by check or money-card) for completion
- 794 of each protocol-specified visit, for a maximum of \$160. If there are extenuating circumstances,
- 795 and the subject is unable to complete study visits without additional funds for travel costs,
- 796 additional funds may be provided.

797 4.9 **Study Costs**

- 798 The subject or his/her insurance provider will be responsible for the costs that are considered 799 standard care.
- 800

801 Because the treatment used in the study is not standard of care, the enrollment, 4-, 8, and 16-week

- 802 follow-up visits will be paid for by the study. The cost of the binocular game treatment related
- 803 equipment will also be paid for by the study; however the iPad will need to be returned upon study completion.
- 804
- 805
- 806 Changes in spectacle correction if done (see section 4.3) will be paid for by the study.
- 807

808 **General Considerations** 4.10

- 809 The study is being conducted in compliance with the policies described in the study policies
- 810 document, with the ethical principles that have their origin in the Declaration of Helsinki, with the 811 protocol described herein, and with the standards of Good Clinical Practice.
- 812
- 813 Data will be directly collected in electronic CRFs, which will be considered the source data.
- 814
- 815 A risk-based monitoring approach will be followed, consistent with the FDA "Guidance for

Industry Oversight of Clinical Investigations — A Risk-Based Approach to Monitoring" (August 816

817 2013).

- 818 **CHAPTER 5: SAMPLE SIZE ESTIMATION AND STATISTICAL ANALYSIS**
- 819

The approach to sample size estimation and the statistical analyses are summarized below. A

820 821 detailed Statistical Analysis Plan document will be written and finalized prior to any tabulation or

822 analysis of study outcome data.

823 5.1 **Definition of Subject Cohorts**

- 824 The study will enroll two cohorts of subjects with identical eligibility criteria, apart from age at time of randomization: 825
 - Younger cohort: Children aged 4 to <7 years
 - Older cohort: Children aged 7 to <13 years •
- 827 828

826

829 Compliance may differ by age; therefore, we believe that there could be a differential treatment 830 effect between age groups. If the binocular game is not as appealing to younger children with some

831 not being able to play the game very well, it is possible that the treatment response with binocular

832 therapy may be reduced in this age group due to poorer compliance with game play compared with

833 the older cohort. The opposite may be true as well. Therefore, the current study will be powered

834 for two separate age cohorts according to the criteria listed above.

835 5.2 **Sample Size Estimation**

836 Sample size estimates for each age cohort were based on data from previous PEDIG studies (ATS3²⁸, ATS5²⁷, and ATS18²⁵), and data from a preliminary pilot study for subjects treated with 837 838 the Dig Rush game on an iPad device (E. Birch Study²⁶) limited to subjects meeting the eligibility 839 criteria for the current protocol.

840 5.2.1 Younger Cohort (Children 4 to <7 years of age)

841 Control Group – Continued Spectacle Correction Alone

842 To estimate the treatment effect in our study for those randomized to continued spectacles alone 843 after stability, data were reviewed from subjects aged 3 to <7 years who were randomly assigned to 844 continue spectacle correction alone in a previous PEDIG study (ATS5, see Table 1). After

845 adjusting for baseline VA, the mean change in VA at 5 weeks was 0.55 logMAR lines (95%

846 confidence interval (CI): 0.19 to 0.90 logMAR lines) with standard deviation 1.28 logMAR lines

- 847 (95% confidence interval (CI): 1.07 to 1.58 logMAR lines).
- 848

849 Given the more stringent criteria for assessing VA stability with spectacles and shorter outcome

850 time in the current study as compared to the previous study, we anticipate that the magnitude and

851 standard deviation of VA improvement after 4 weeks in the current study will be smaller than those

- 852 in Table 1.
- 853
- 854 Binocular Treatment Group (Dig Rush Game):
- 855 Data from 2 studies were reviewed: (1) preliminary pilot data for subjects randomly assigned to 4
- 856 weeks of binocular treatment with the Dig Rush game on an iPad device (E. Birch Study) and (2)

857 data from a previous PEDIG trial (ATS18) for subjects randomly assigned to binocular treatment

858 with the Hess falling blocks game on an iPad device (Table 1). Based on the more conservative

- 859 estimates from ATS18, a mean VA change at 4 weeks of 1.09 lines (95% CI: 0.63 to 1.55 lines),
- with standard deviation 1.32 logMAR lines (95% CI: 1.06 to 1.74 logMAR lines) after adjusting for 860
- 861 baseline VA might be expected. However, we anticipate that the magnitude of VA improvement
- 862 after 4 weeks in the current study will be somewhat larger than that in ATS18, due to better
- 863 compliance.
- 864 865

	J	Change in Amblyopic Eye VA			
		at the 4 or 5 Week Visit			
		(logMAR Lines) [‡]			
Cohort	Ν	Mean Change (95% CI)	SD Change (95% CI)		
Spectacle Correction Alone:					
ATS5: Age 3 to <7 years [†]	53	0.55 (0.19 to 0.90)	1.28 (1.07 to 1.58)		
No prior amblyopia treatment	50	0.54 (0.17 to 0.91)	1.32 (1.10 to 1.64)		
Prior amblyopia treatment	3	0.67 (-2.21 to 3.54)	0.39 (0.20 to 2.45)		
Binocular Treatment:					
E. Birch Study (Age 4 to <7 years) ^	9	1.67 (0.73 to 2.61)	1.19 (0.80 to 2.28)		
ATS18 (Age 5 to <7 years) §	34	1.09 (0.63 to 1.55)	1.32 (1.06 to 1.74)		
No prior amblyopia treatment	19	1.47 (0.73 to 2.22)	1.54 (1.16 to 2.28)		
Prior amblyopia treatment	15	0.60 (0.15 to 1.05)	0.81 (0.59 to 1.28)		

866 Table 1: Previous Study Data from Subjects Aged 3 to <7 Years of Age

[‡] Positive values indicate improvement. Mean and SD adjusted for baseline visual acuity.

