600 Subjects assigned to the binocular treatment group will be prescribed the Dig Rush game to play for 601 1 hour per day, 5 days a week for 8 weeks. Parents of subjects will be instructed that the 1 hour of 602 daily treatment should be completed in a single 60-minute session, but if this is not possible for 603 whatever reason, the treatment may be divided into shorter sessions totaling 1 hour per day.

604

All subjects in the study will play the Dig Rush game presented on an iPad while wearing red/green (anaglyph) glasses (over current spectacle correction, if applicable) with the green filter placed over the amblyopic eye. The subject should be instructed to hold the iPad at his/her usual reading distance. Some game elements are only visible to the fellow eye viewing through the red lens, while other game elements are only visible to the amblyopic eye viewing through the green lens. Image contrast varies depending on depth of amblyopia to ensure stimulation of the amblyopic eye and binocular game play.

612

613 Contrast of the game elements in the amblyopic eye will be at 100% throughout the study. Contrast

of game elements seen by the fellow eye will begin at 20% at the start of the study and will increase

or decrease automatically in increments from the last contrast level (e.g., 20% to 22%) based on the

616 subject's performance and duration of game play.

617 **3.2** Continued Spectacle Correction Group

618 Subjects assigned to the continued spectacle wear group will continue wearing their appropriate

619 spectacle correction (if required) for all waking hours, 7 days per week for 8 weeks. Subjects

620 assigned to the continued spectacle wear group will be offered binocular treatment for 8 weeks after

621 the initial 8 weeks of the study has been completed. Subjects in the continued spectacle correction

- 622 group that choose to continue with binocular treatment after 8 weeks will return for a follow-up
- 623 visit at 16 weeks.

624 **3.3** Compliance

Parents will be asked to complete a compliance calendar by manually recording the number of minutes that the child played the game each day, and/or how long the child has worn the spectacle correction. The investigator will review the calendars at each follow-up visit. The amount of time the game is played will also be recorded automatically during game play by the iPad. These data will be downloaded at the Jaeb Center when the iPad is returned after the study.

630 **3.4** Phone Call

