631 Site personnel will call all subjects at 1 week (7 to 13 days) to encourage compliance with treatment

and to confirm that there are no technical problems playing the binocular game for those assigned to

633 binocular treatment. Site personnel will call subjects in the continued spectacle treatment group

634 who switch to binocular treatment at 9 weeks (7 to 13 days after the 8-week visit), again to

635 encourage compliance with treatment and to confirm that there are no technical problems playing

636 the binocular game for those assigned to binocular treatment.

637 **3.5 Follow-up Visit Schedule**

638 The follow-up schedule is timed from randomization as follows:

- 639
 1-week phone call (7 to 13 days from randomization) to inquire about issues with the
 640
 641
 641
 641
 641
- 641 be completed by site personnel)
- 4 weeks ± 1 week (primary outcome)

- 643 8 weeks ± 1 week (secondary outcome)
- Binocular final visit
 - Spectacle group switched to binocular treatment and followed for 8 weeks
- 9-week phone call (Spectacle group only: 7 to 13 days from 8-week exam) to inquire about
 issues with the binocular game (if applicable) and to encourage compliance with treatment
 for all groups (to be completed by site personnel)
- 649
 16 weeks ± 1 week (final visit for group originally randomized to continued spectacle treatment who were switched to binocular treatment)
- 651

652 Additional non-study visits can be performed at the discretion of the investigator.

653 **3.6 Resolution of Amblyopia**

Subjects achieving amblyopic-eye VA equal to or better (0 lines or more lines better) than the better
of the fellow-eye VA at baseline or 4-week visit, will be considered to have resolved and may
discontinue binocular treatment, although these subjects will still return for all remaining follow-up
exams.

658 3.7 Optional Post 8-week Treatment

659 For children originally randomized to binocular treatment, the study ends at 8 weeks.

660

661 Children who were originally assigned to continued spectacle treatment will be offered binocular

treatment for 8 weeks following the 8-week visit. The study will end at the 8-week exam for

663 children who choose not to receive binocular treatment. Children receiving binocular treatment at

the 8 week exam will return at 16 weeks for a follow-up visit. The study will end for these children

at the 16-week visit.

666 **3.8 Follow-up Visit Testing Procedures**

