667 Subjects will be seen at follow-up visits as outlined in *section 3.5*. A Masked Examiner must

668 complete distance VA and stereoacuity testing at these visits (*section 3.8.1*). All procedures will be

669 performed with the subject's current spectacle correction. If a subject currently wears spectacles

but is not wearing them at the follow-up examination for whatever reason, testing must be

- 671 performed in trial frames.
- 672

673 Prior to the Masked Examiner entering the room, subjects and parents should be instructed not to 674 discuss their treatment with the Masked Examiner.

675

676 The following study procedures are performed at each visit:

677 678

- 1. ATS Diplopia Questionnaire
- The child and parent(s) will be specifically questioned regarding the presence and frequency of any diplopia within the last 2 weeks using a standardized diplopia assessment (*see ATS Miscellaneous Testing Procedures Manual*). The diplopia assessment must be performed prior to any other testing during the exam.

684		
685	2.	Symptom Survey
686		• The child and parent(s) will complete a 5-item symptom survey regarding the
687		presence of various ocular symptoms within the past 2 weeks (see ATS
688		Miscellaneous Testing Procedures Manual). The symptom survey must be
689		performed prior to any other testing during the exam.
690		
691	3.	Distance VA Testing (masked):
692		• Monocular distance VA testing will be performed in the current spectacle correction in
693		each eye using the same VA testing method that was used at enrollment, as described in
694		the ATS Testing Procedures Manual.
695		• The ATS HOTV testing protocol will always be used to test VA in the younger
696		age cohort (4 to <7 years at enrollment) whereas the E-ETDRS protocol will
697		always be used to test VA in the older cohort (7 to <13 years at enrollment).
698		 Testing must be completed without cycloplegia.
699		
700	4.	Stereoacuity Testing (masked):
701		• Near stereoacuity will be tested in habitual current refractive correction using the Randot
702		Butterfly test and Randot Preschool Stereoacuity test at near (1/3 meter).
703	_	
704	5.	Ocular Alignment Testing:
705		• Ocular alignment will be assessed in the current spectacle correction by the cover test,
706		simultaneous prism and cover test (SPCT) (if strabismus is present on cover testing), and
707		prism and alternate cover test (PACT) in primary gaze at distance (3 meters) and at near

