5.4.3.3 Diplopia

1037 The proportion of subjects with each level of diplopia frequency will be reported by treatment group 1038 at 4 weeks. Data will also be tabulated based on the maximum frequency of diplopia reported by 1039 treatment group. The change in diplopia frequency level from baseline to 4 weeks will be compared 1040 between treatment groups using the exact Wilcoxon rank-sum test.

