5.4.3.4 Adverse Symptoms 1041

1042 The child and parent(s) will complete a 5-item symptom survey regarding the presence of various 1043 ocular symptoms within the past 2 weeks at enrollment and at each visit. The distribution of scores 1044 on each symptom survey item will be described for the enrollment exam and the 4-week exam for

each treatment group. The distribution of change in scores on each symptom survey item will also 1045 1046 be described for each treatment group.

1047 5.4.4 Outcomes at 8 Weeks

1048 As secondary analyses, all analyses described above will be repeated using data obtained from the 1049 8-week visit.

1050 5.4.5 Exploratory Analyses 1051

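### A 2-week look-back at visits 4 weeks apart leaves at least half of the 8-week treatment period, including the first week of play, outside the diplopia and symptom data

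*Protocol*

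**What the plan says.** **Instruments.** Protocol 3.8, item 1, asks child and parent at each follow-up visit about the presence and "frequency of any diplopia within the last 2 weeks using a standardized diplopia assessment". Item 2 gives a five-item survey on the "presence of various ocular symptoms within the past 2 weeks". Section 5.4.3.4 repeats that look-back for the analysis: "ocular symptoms within the past 2 weeks at enrollment and at each visit". Enrollment (2.4) uses the same two instruments and the same 2 weeks.

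**Timing.** Section 3.1 prescribes play for "1 hour per day, 5 days a week for 8 weeks". Section 3.5 sets the randomized-phase visits at 4 and 8 weeks, each within a week either way. Controls who take up the game at 8 weeks have one further visit, at 16 weeks.

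**Other contacts.** Under 3.4, "Site personnel will call all subjects at 1 week (7 to 13 days) to encourage compliance with treatment" and to check for technical problems; 3.5 adds an inquiry about problems with the game. Switchers get a similar call at 9 weeks. Section 4.5.1 advises parents to bring in a child who develops diplopia or a deviation, but 3.10 collects no study data at non-study visits.

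**Analysis.** SAP 4.4.3 and 4.4.4 compare scores, and changes from baseline, at 4 and 8 weeks, and name no other data source. Protocol 5.4.3.3 adds that "Data will also be tabulated based on the maximum frequency of diplopia reported by" treatment group; SAP 4.4.3 does not carry that table.

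**The concern.** Diplopia and the symptom survey are the patient-reported safety outcomes, and their look-back is half as long as the interval between visits. If trouble with a new dichoptic game comes early and passes, an on-schedule 4-week visit will not record it. A child with double vision in week 1 who stops playing and is well from day 14 answers truthfully that there was none in the last 2 weeks, and enters the 4-week comparison at the lowest frequency level.

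The protocol foresees such a case: 4.5.1 allows for treatment to be discontinued because of diplopia. What is at stake is whether the reported comparison describes the treatment period or only the fortnight before each visit.

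**Working it through.** The documents state no coverage figure, so there is none to reproduce. The check is a count of days.

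**Inputs**
- Look-back: 14 days (Protocol 3.8, items 1 and 2)
- Prescribed play: 8 weeks = 56 days, numbered 0 to 55 (3.1), assumed to start at randomization
- First visit v1: day 28, permitted 21 to 35 (3.5)
- Second visit v2: day 56, permitted 49 to 63 (3.5)
- Week-1 call: days 7 to 13 (3.4)

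A visit on day v covers days v − 14 to v − 1.

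**On schedule**
- v1 = 28 covers days 14–27; v2 = 56 covers days 42–55.
- Covered: 14 + 14 = 28 days; 28/56 = 50%.
- Not covered: days 0–13 and 28–41.

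**All permitted dates**
- The two look-backs never overlap: the latest first visit covers up to day 34, and the earliest second visit covers from 49 − 14 = day 35.
- A second visit after day 56 spends part of its look-back after prescribed play. Covered treatment days = 14 + 14 − max(0, v2 − 56).
- v2 of 56 or earlier: 28 days (50%). v2 = 63: 28 − 7 = 21 days; 21/56 = 37.5%.
- So 21 to 28 days are covered, and at least half is always uncovered.

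**First two weeks**
- Days covered among 0–13 = max(0, 28 − v1).
- v1 = 28 or later: 0 days. v1 = 21: 7 days (days 7–13).
- The earliest look-back starts on day 21 − 14 = 7, so no in-window visit covers days 0–6.

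**Controls who switch**
- One visit follows 56 days of play. On schedule, 14/56 = 25% is covered.

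**Could another route fill the gap?**
- Week-1 call: diplopia and symptoms are not among its specified content, and no recording for analysis is described.
- Unscheduled visit under 4.5.1: 3.10 excludes its data.
- Adverse events: Protocol 4.6 refers to local IRB reporting and describes no study-wide collection.
- Treatment deviations: SAP 4.5, item 7, counts crossover and alternative treatment, not stopping play because of symptoms.
- iPad logs: they give time played and contrast, not the reason for stopping.

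None of these is specified to enter the comparisons in SAP 4.4.3 and 4.4.4.

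**The case against.** A good deal can be said for the plan. The 2-week look-back matches enrollment, so change scores compare equal periods, and short recall is sensible when respondents include 4-year-olds. Persistent or recurrent symptoms are still captured. Ocular alignment and fellow-eye acuity are measured at the visit and are unaffected. The protocol expects diplopia to be rare from the previous binocular-game trial and classes the study as minimal risk. All of this stands. It argues for keeping the instrument and for treating the point as a modest improvement. It does not put the missing days into the data.

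Four stronger readings are tempting, and the documents do not support them:

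- *The first two weeks are never observed.* That is strict only when the first visit is on day 28 or later. A visit on days 21 to 27 recovers 7 down to 1 of days 7–13.
- *The study would not hear of early trouble.* Section 3.5 has the caller ask about problems with the game, and 4.5.1 sends a child with diplopia to the investigator and has a Protocol Chair called if treatment is to stop. The gap is in recorded, analyzable data, not in contact.
- *The loss occurs only in the binocular arm.* The look-back is the same in both arms, and passing symptoms in controls are missed too. Only the response of stopping play is specific to one arm.
- *Including late visits in the safety analyses makes coverage far worse.* A look-back wholly after prescribed play needs a visit on day 56 + 14 = 70 or later, beyond the protocol limit of day 63. Keeping such visits under SAP 4.4 retains data and is not a defect.

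**Conclusion.** The point holds for the structured data. With in-window visits, the diplopia and symptom results rest on 21 to 28 of 56 treatment days, 28 when visits are on schedule. Week 1 is always outside, and week 2 is outside in whole or in part unless the first visit is on day 21. Switchers have about a quarter of their play covered.

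Short-lived early diplopia, headache or eyestrain is therefore missed in both arms. Since only binocular-arm children can end an exposure to play that troubles them, the randomized comparison may lean toward no harm. That direction is an inference. The documents give no rate of passing early symptoms or of stopping because of them, so the size cannot be estimated and may be small.

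The counts assume that play starts at randomization and that answers respect the 2-week limit. The primary outcome is not touched. This is a cheap improvement to safety ascertainment, not a flaw in the efficacy comparison.

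**What to change.** **If data can still be collected**
- At the week-1 call, in both arms, add recorded items on diplopia, headache, eyestrain and blurry vision, worded 'since starting the study'. A 2-week item asked on days 7 to 13 would reach back before randomization. At the 9-week call for switchers, use 'since starting the game'.
- Keep the 2-week instruments unchanged for the baseline-comparable change analysis.
- At each follow-up visit add one question to child and parent, 'any double vision since the last contact?', with a follow-up on whether play was stopped for it where that applies.
- In SAP 4.4.3 and 4.4.4, report by arm the worst frequency over post-baseline contacts, including the maximum-frequency diplopia table promised in Protocol 5.4.3.3. Keep this descriptive: a maximum over several contacts is not comparable with a single baseline value.

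For presence of diplopia, completed contacts would then cover all 56 days. For headache, eyestrain and blurry vision, on-schedule coverage would rise from 28 to between 28 + 7 = 35 and 28 + 13 = 41 days (63% to 73%).

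**If collection is complete**, as the SAP revision history suggests at least for the younger cohort, produce the maximum-frequency diplopia table from visit data and state that the diplopia and symptom results describe only the 2 weeks before each visit.

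**Cost.** A few questions on calls already made, one question per visit and one table. The added visit question has longer recall and is less precise, so it supplements the 2-week instrument and does not replace it.
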